enzalutamide 160 mg QD. Twelve patients have received CORT125281 in combination with enzalutamide, and 2 patients discontinued the study during the enzalutamide lead-in and did not receive CORT125281. In Cohort 1, two patients received CORT125281 180 mg BID with enzalutamide. Both patients experienced dose-limiting toxicities (DLTs), including Grade 3 fatigue (n=1), and the concurrent SAEs of Grade 3 fatigue and Grade 3 musculoskeletal pain (n=1); thus CORT125281 180 mg BID was deemed intolerable. A lower dose (CORT125281 140 mg BID) was evaluated in Cohort 2. In Cohort 2, 1 of 3 patients experienced a DLT (SAE of Grade 3 acute pancreatitis). After the third patient enrolled to Cohort 2, an interim assessment of PK and safety was conducted. Based upon the absence of a clinically significant drug interaction of CORT125281 on enzalutamide exposure, enrollment to the subsequent cohort was initiated to further evaluate the CORT125281 140 mg BID dose level without the enzalutamide lead-in. Seven patients have been enrolled to Cohort 3. One patient was not evaluable for DLTs due to disease progression during Cycle 1. Of the 6 remaining patients, no DLTs were observed and the dose was considered tolerable.

Twelve patients (100%) who have received at least 1 dose of CORT125281 in combination with enzalutamide reported greater than 1 TEAE. Five patients (42%) reported TEAEs of Grade 3 or greater considered related to CORT125281; the most frequent TEAE of Grade 3 or greater was fatigue (n=2; 17%). An alternative schedule (once daily [QD] dosing of CORT125281) is planned to optimize the biologically active dose prior to proceeding to the Phase 2 expansion cohorts.

CORT125281-602

In accordance with the study design, 6 healthy subjects received a single oral dose of [¹⁴C]-CORT125281 360 mg (6 × 60-mg capsules). No TEAEs were reported in this study.

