5.4.2 Dose-Determination Phase Segment 2 (Double-Blind)

In Segment 2, all patients will start treatment with CORT125281 240 mg QD on Cycle 1 Day 1. Patients will continue on their current dose of enzalutamide during the Screening Period and at the initiation of CORT125281. Beginning on Cycle 1 Day 16, the dose of the investigational agent will be increased in 40-mg increments every 2 weeks, as tolerated, with either CORT125281 (Arm A; N=12) to a maximum dose of CORT125281 320 mg QD or with placebo (Arm B; N=4) (Table 8). If any planned dose escalation is postponed due to transient intolerable Grade 2 toxicity or scheduling conflicts (delays not due to toxicity), the dose may be escalated within 14 days of the planned escalation.

- Arm A (N=12): CORT125281 240 mg QD under fed conditions with upward dose titration in combination with enzalutamide. CORT125281 will be increased in 40-mg increments every 2 weeks (+14-day window) based upon tolerability to a maximum dose of 320 mg QD (Table 8).
 - Cycle 1 Day 1: CORT125281 240 mg QD
 - Cycle 1 Day 16 (+14-day window): CORT125281 280 mg QD
 - Cycle 2 Day 2 to Cycle 2 Day 16 (+14-day window): CORT125281 320 mg QD

- Arm B (N=4): CORT125281 240 mg QD under fed conditions, with an increase in the number of placebo capsules every 2 weeks (+14-day window) (Table 8).
 - Cycle 1 Day 1: CORT125281 240 mg QD
 - Cycle 1 Day 16 (+14-day window): CORT125281 240 mg QD
 - Cycle 2 Day 2 to Cycle 2 Day 16 (+14-day window): CORT125281 240 mg QD

Table 8 CORT125281 Upward Dose Titration for Dose-Determination Phase Segment 2

Dose Level	Resulting CORT125281 Dosage (QD)		Open-Label Bottle (CORT125281)	Blind-Label Bottle (CORT125281 or Placebo) ^a
	Arm A	Arm B		
1 (Starting Dose)	240 mg	240 mg	6 capsules	0 capsules
+1 (First Increase)	280 mg	240 mg	6 capsules	1 capsule
+2 (Second Increase)	320 mg	240 mg	6 capsules	2 capsules

QD, once daily.

Note: The CORT125281 dose will be escalated in 2-week intervals unless there are intolerable Grade 2 toxicities, dose-limiting toxicities, or Grade 3 or greater toxicities attributed to CORT125281 (Section 5.7).

^a. Note: The blind-label bottle contains blinded capsules (CORT125281 [Arm A] or placebo [Arm B]).

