During the double-blind portion of the Dose-Determination Phase (ie, Segment 2), an unblinded Medical Monitor independent of the study team will provide additional oversight for the study, including review of serious unexpected AEs considered related to either CORT125281 or enzalutamide and DLTs.

The DLT-evaluation period will extend from the first dose of CORT125281 through the completion of Cycle 3. The DLT-Evaluable Population will include all patients in Segment 2 who received at least 1 dose of CORT125281 and fulfilled at least 1 of the following:

- Completed 3 cycles of treatment with CORT125281 + enzalutamide and received at least 75% of the study regimen
- Experience a DLT

Patients who are non-evaluable for DLTs will include the following:

- Received <75% of the study regimen for reasons other than toxicity
- Patients who withdraw from the study prior to completion of Cycle 3 for reasons other than toxicity (eg, lost to follow-up, withdrawal of consent, or disease progression)

Patients who are non-evaluable for DLTs will be allowed to continue in the study and receive CORT125281 in combination with enzalutamide. Patients who are non-evaluable for DLTs may be replaced to allow a sufficient number of patients to evaluate DLTs (Section 9.4.1).

After all patients complete 3 cycles of treatment or discontinue treatment, the data will be unblinded and the DRC will meet to review the safety and available PK and PD data. The DRC will evaluate the frequency of DLTs, the DLT rate (number of DLTs in DLT-evaluable patients per week [7-day period] during the DLT-evaluation period), and overall tolerability in their assessment of the dose titration regimen as the Phase 2 RD.

If the DLT rate for the regimen is $\geq 33\%$, alternative titration schemes may be considered as the regimen for the RD, such as greater time increments between dose escalations or limiting the upper range of the regimen to those dose levels corresponding to a DLT rate of $< 33\%$. Once the DRC has determined the RD, patients assigned to Arm B who have not experienced dose reductions due to toxicity will then escalate the CORT125281 dose per the recommended upward titration regimen.

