7.3 Combination Treatment Period

Cycle 1 will begin the day after Screening is complete for patients in Dose-Determination Phase Segment 2 and the following patients in the Expansion Phase:

- Patients in the Abi-Resistant Cohort who are NOT in the Food-Effect Subcohort
- All patients in the ARant-Resistant Cohort

Cycle 1 will begin the day after the Lead-In Period is complete for all patients in Dose-Determination Phase Segment 1 and patients in the Expansion Phase Food-Effect Subcohort.

The acceptable visit window is ± 1 day for all visits during Cycle 1, unless the window spans a weekend; and ± 3 days for all other cycles. Visit windows are relative to Cycle 1 Day 1.

Study-related activities to be performed at the in-clinic visits are described in [Appendix A](#).

The following assessments should be performed during each in-clinic visit during the Combination Treatment Period:

- Record concomitant medications
- Record AEs
- Physical examination
- Vital signs
- ECOG performance status
- Local laboratory tests (see [Table 11](#) for details)
 - CBC with differential
 - Chemistry, including LDH
- Review diary card

The following assessments should be performed on Day 1 of each cycle:

- Measure body weight
- Triplicate 12-lead ECG (Day 1 of Cycle 1 and Cycle 3 only, and Day 15 of Cycle 1)
- Local laboratory tests (see [Table 11](#) for details)
 - PT, aPTT, and INR (Day 1 of Cycles 1 through 3)
 - Urinalysis (Day 1 of Cycles 1 through 3 and every third cycle after Cycle 3)
 - TSH, with reflex FT4 and TT3 or FT3 (every 3 months for the first year, starting with Day 1 of Cycle 3, and then every 6 months after the first year)
 - PSA
 - Serum amylase and lipase (each study visit through completion of Cycle 3, then every 3 months until completion of 12 months of study treatment)
- Dispense study treatment
- Provide patient diary card
- Study treatment accountability

Following the baseline/pre-treatment assessment, radiographic tumor assessments should be performed 8 weeks from the first dose of study treatment (CORT125281 or on-study enzalutamide, whichever is earlier), and then every 8 weeks for the first 24 weeks and every 12 weeks thereafter. For on-study scans, a window of ± 14 days is acceptable with the timing of the scans based on Cycle 1 Day 1.

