aPTT, activated partial thromboplastin time; CBC, complete blood count; CT, computed tomography; DRC, Data Review Committee; ECG, electrocardiogram; ECOG, Eastern Cooperative Oncology Group; EOT, End-of-Treatment; FACT-P, Functional Assessment of Cancer Therapy-Prostate; FT3, free triiodothyronine; FT4, free thyroxine; INR, international normalized ratio; LDH, lactic dehydrogenase; Mnth, month; MRI, magnetic resonance imaging; PSA, prostate-specific antigen; PRO, patient-reported outcomes; PT, prothrombin time; QoL, quality of life; TSH, thyroid-stimulating hormone; TT3, total triiodothyronine.

Note: In all parts of the study, a cycle of therapy is considered to be 28 days with no rest periods in between cycles. All procedures within a cycle should be counted by calendar day from Day 1 of that cycle. A 2-day window will be allowed for study visits.

- a. The Lead-In Period only applies to patients in Dose-Determination Phase Segment 1 and patients in the Expansion Phase Food-Effect Subcohort. Lead-in duration is 28 days in Dose-Determination Phase Segment 1, and 7 days for patients in the Expansion Phase Food-Effect Subcohort. When a recommended dose of enzalutamide is determined by the DRC, the DRC may recommend discontinuing the lead-in for subsequent cohorts.
- b. Upon discontinuation of CORT125281, if the patient continues on enzalutamide alone (Section 5.7.1.1) and all toxicities attributed to CORT125281 have resolved, visit frequency can be decreased per the Investigator's standard of care. The patient should come for their regularly scheduled visit (the subsequent cycle) after discontinuing CORT125281. After this visit, visits can be conducted less frequently per Investigator discretion, but at a minimum every 3 cycles while on enzalutamide alone; at these visits they will have the assessments listed in the "Cycle 4 & Beyond" column. After discontinuation of enzalutamide, the patient will return for their EOT Visit, and then for an EOT +30 Days Visit.
- c. Phone follow-up for overall survival (ie, the date and cause of death, and post-treatment information) will continue every 4 months until the study endpoints are met or 2 years from the date that the last patient enrolls in the study (whichever is later).

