- d. Consent to provide optional or mandatory (for a subset of patients) paired tissue biopsy material for determination of glucocorticoid receptor expression and other exploratory biomarkers is required for eligibility; the first biopsy will be obtained within 6 weeks prior to the first dose of study treatment (enzalutamide and/or CORT125281). An additional paired biopsy will be collected at Cycle 2 Day 1 (-14 days). It is preferred that this biopsy be collected from the same lesion as the baseline sample, if sufficient tissue remains and if logistically feasible. Optional: consent to provide on-study biopsy 1) obtained during procedure conducted as standard of care; or 2) at the time of disease progression.
- e. To be performed on Cycle 1 Day -28 for patients enrolled in Cohort 1 of Dose-Determination Phase Segment 1 with lead-in, Cycle 1 Day -7 for patients enrolled in the Expansion Phase Food-Effect Subcohort, and Cycle 1 Day 1 for non-food-effect patients enrolled in the Abi-Resistant and ARant-Resistant Cohorts of the Expansion Phase.
- f. To be performed and reviewed prior to the first dose of CORT125281. Laboratory assessments (CBC with differential, chemistry [including LDH], PSA, and urinalysis) may be collected on either Cycle 1 Day -1 or Cycle 1 Day 1 based upon logistics and convenience to the sites and patients.
- g. Complete physical examinations should be performed at Screening, Day 1 of each cycle, and the End-of-Treatment Visit. Limited physical examinations should be performed at all other visits.
- h. Perform before dosing and approximately 2 hours post-dose (± 10 minutes) on Cycle 1 Day 1 and Cycle 1 Day 15 (for all patients) and Cycle 3 Day 1 (for patients in Dose-Determination Phase Segment 1 only).
- i. Complete blood count will also be used to assess the neutrophil-to-lymphocyte ratio and relative abundance of other cells.
- j. Screening safety laboratory assessments must be performed within 7 days of the start of the Lead-In Period. For patients who are NOT participating in the Lead-In Period, Screening CBC and chemistry do not need to be repeated if they were collected within 7 days of Cycle 1 Day 1.
- k. Every 3 months until completion of 12 months of study treatment, starting on Cycle 6 Day 1. Note: For patients continuing on enzalutamide alone, sample collections for amylase and lipase will not be required at these visits.

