8.8. Dose Limiting Toxicity (DLT) Analyses

Prior to data unblinding, investigators will review AEs that occurred during the DLT-evaluation period and determine AEs that meet the DLT definition.

Dose-Determination Phase Segment 1

DLT analyses will be performed for DLT-evaluable population for patients in Dose-Determination Phase Segment 1, which include all patients who complete at least 1 cycle (4 weeks) of study treatment for segment 1 patients and have received $\geq 75\%$ of doses for both exicorilant and enzalutamide during the DLT evaluation period, or who discontinue treatment due to toxicity.

Three patient cohorts were enrolled in Dose-Determination Phase Segment 1, which are

- (1) Cohort 1: exicorilant 180mg BID/ enzalutamide 160 mg QD
- (2) Cohort 2: exicorilant 140mg BID/ enzalutamide 160 mg QD
- (3) Cohort 3: exicorilant 140mg BID/ enzalutamide 160 mg QD; No enzalutamide lead-in period

Number of patients with at least 1 DLT and number of DLTs will also be summarized by cohort, and overall.

Dose-Determination Phase Segment 2

DLT analyses will be performed for DLT-evaluable population for patients in Dose-Determination Phase Segment 2, which include all patients who complete at least 3 cycles (12 weeks) of study treatment for segment 2 patients and have received $\geq 75\%$ of doses for both exicorilant and enzalutamide during the DLT evaluation period, (or equivalently, received ≥ 63 days of doses during the first 12 weeks for segment 2 patients), or who discontinue treatment due to toxicity.

Three study regimens will be evaluated for Segment 2 Arm A during the DLT-evaluation period, which are

- (1) Regimen 1: 240 mg exicorilant + enzalutamide
- (2) Regimen 2: 240-280 mg exicorilant + enzalutamide
- (3) Regimen 3: 240-280-320 mg exicorilant + enzalutamide

DLT rate will be calculated for each study arm, study regimen and overall. The DLT rate for each study regimen is calculated as the ratio of the number of DLT-evaluable patients who experience at least one DLT during the treatment of any dose level of exicorilant from that study regimen to all DLT-evaluable patients.

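### Table 16 leaves Days 58 to 84 of the Segment 2 DLT window without a scheduled amylase or lipase test, and it does not agree with Section 7.3 on how long early testing runs

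*Protocol*

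**What the plan says.** Three parts of the protocol bear on this.

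- **Section 7.3** lists "Serum amylase and lipase (each study visit through completion of Cycle 3, then every 3 months until completion of 12 months of study treatment"). The line stands under a heading that reads "The following assessments should be performed on Day 1 of each cycle", so it is unclear whether it reaches visits that are not on Day 1.
- **Appendix A, Table 16** marks amylase and lipase at Screening, at every Cycle 1 and Cycle 2 visit, and on Cycle 3 Day 1. The cells for Cycle 4 & Beyond, EOT and EOT +30 Days are blank. The later series is governed by footnote k: "Every 3 months until completion of 12 months of study treatment, starting on Cycle 6 Day 1".
- **Section 5.4.2** sets the Segment 2 window: "The DLT-evaluation period will extend from the first dose of CORT125281 through the completion of Cycle 3".

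On the toxicity itself, Section 1.3.2.1 reports that in Segment 1 Cohort 2 "1 of 3 patients experienced a DLT (SAE of Grade 3 acute pancreatitis"). Section 5.5 counts a Grade 3 or greater non-hematologic toxicity as a DLT if it is at least two grades above baseline, possibly or probably drug-related, and not due to disease. Its exceptions name several laboratory changes, but not amylase or lipase.

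**The concern.** DLTs are the primary endpoint, and the Segment 2 count informs the choice of the recommended dose. Amylase and lipase were added to the laboratory list in Amendment 5 (Appendix E), which also introduced Segment 2 and its three-cycle window. The Table 16 schedule does not reach the end of that window, and Section 7.3 can be read as going further than the table does.

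The Cycle 4 Day 1 chemistry does not obviously fill the gap. Table 11 lists the two enzymes under Other, not under Serum Chemistry. Section 7.1 names them as part of screening chemistry, whereas Sections 7.3 and 7.4 name only LDH as included in chemistry on treatment and at EOT.

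A site that follows Table 16 as written would have no enzyme result for the last part of the window. A laboratory-only event there could go unseen and uncounted.

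**Working it through.** **Inputs**

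- Cycle length, Table 16 note: "a cycle of therapy is considered to be 28 days with no rest periods in between cycles".
- Segment 2 window: Protocol 5.4.2 and 9.2 (three cycles, at least 84 days), and SAP 8.8 ("complete at least 3 cycles (12 weeks) of study treatment for segment 2 patients").
- Enzyme test days: Table 16 and footnote k.
- Start of 320 mg in Arm A, Section 5.4.2: "Cycle 2 Day 2 to Cycle 2 Day 16 (+14-day window): CORT125281 320 mg QD". Table 16 footnote r puts the first raised dose on the day after the visit.
- PK and PD collections 2 weeks (±2 days) after each escalation: Tables 18 and 21.

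**Step 1. Reproduce the plan's figure.** 3 × 28 = 84 days = 12 weeks. This agrees with Protocol 9.2 and SAP 8.8.

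**Step 2. Place the tests.** Study day = (cycle − 1) × 28 + day. The Table 16 tests fall on Days 1, 8, 15, 22, 29, 43 and 57. Cycle 4 Day 1 is 3 × 28 + 1 = Day 85, with no enzyme test. Cycle 6 Day 1 is 5 × 28 + 1 = Day 141. The gap is 141 − 57 = 84 days.

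**Step 3. Compare with the window.** Days after the last test: 84 − 57 = 27, and 27/84 = 32.1%. This applies to every Segment 2 patient under Table 16. By contrast, the Segment 1 window ends on Day 28, and the Cycle 2 Day 1 test on Day 29 closes it.

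**Step 4. Tests at 320 mg in Arm A (nominal days)**

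| 320 mg starts | Days at 320 mg in window | Table 16 tests at 320 mg in window | PK/PD visit 2 weeks later |
|---|---|---|---|
| Cycle 2 Day 2 (Day 30) | 84 − 30 + 1 = 55 | Days 43 and 57 | Day 44 (42–46) |
| Cycle 2 Day 16 (Day 44) | 84 − 44 + 1 = 41 | Day 57, after 13 days | Day 58 (56–60) |
| Cycle 3 Day 2 (Day 58) | 84 − 58 + 1 = 27 | none | Day 72 (70–74) |

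The last row requires the 14-day allowance to be added to Cycle 2 Day 16 (44 + 14 = 58).

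**Step 5. Apply Section 7.3 literally.** If every visit through Cycle 3 counts, the Day 58 starter is tested at about Day 72, which leaves 84 − 72 = 12 days to the end of the window. The Day 44 starter is tested no later than Day 60, which leaves at least 84 − 60 = 24 days. An on-schedule patient has no visit in Cycle 3 after Day 1, so nothing is added and the 27 days remain. Neither reading puts a scheduled test at the close of the window.

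**Step 6. What one event could change.** Take 12 evaluable Arm A patients and assume the 33% limit in Section 5.4.2 is applied to the proportion of patients with a DLT. Then 4/12 = 33.3% reaches the limit and 3/12 = 25.0% does not. One uncounted patient therefore matters only if the true count sits at that boundary. The documents give no incidence of asymptomatic enzyme rises, so the chance of this cannot be computed.

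Visit windows of ±3 days from Cycle 2 onward shift these days slightly without closing the gap.

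**The case against.** The strongest reply is that the toxicity already seen was a serious clinical event, not a laboratory finding. Adverse events, physical examination and chemistry are scheduled on Cycle 4 Day 1, SAEs are reported within 24 hours, and Section 7.6 allows unscheduled assessments. An isolated enzyme rise becomes a DLT only if it meets the grade, baseline-change and relatedness conditions of Section 5.5. Under Section 8.1.7, a laboratory abnormality that leads to neither dose modification nor withdrawal is reported as an AE at the investigator's discretion. All of this stands, and it confines the point to asymptomatic rises.

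It can also be said that Section 7.3 and Table 16 agree for on-schedule patients, because Cycle 3 Day 1 is their only Cycle 3 visit and the 84-day gap is three cycles. No passage ranks Table 16 above Section 7. This is fair as to a literal conflict. It does not supply an enzyme value for the end of the window.

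A reader might infer more than the documents support:

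- **That late escalators have no test at 320 mg within the window.** This holds only for a Cycle 3 Day 2 start, and only if Section 7.3 does not cover the PK/PD visit about two weeks later. If the delay is counted from Cycle 2 Day 2, the latest start is Day 44, with a test after 13 days. Section 6.6 and Table 16 footnote r give Cycle 2 Day 1 or Day 15 as example days before the second escalation.
- **That the most exposed patients are those delayed for toxicity.** Section 5.4.2 also allows delay for scheduling conflicts.
- **That the DLT count is biased low by a known amount.** No size can be derived. The single pancreatitis event arose on fasted twice-daily dosing, and six later evaluable patients at the same 140 mg BID dose had no DLT.

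**Conclusion.** The point holds in a limited form. Following Table 16, the last 27 of 84 days (32%) of the Segment 2 DLT window have no scheduled amylase or lipase test during them or at their close. Section 7.3 is worded differently, and its reach is ambiguous. What is at risk is completeness of the primary DLT endpoint for asymptomatic Grade 3 or greater enzyme rises judged drug-related. Detection of symptomatic pancreatitis is not at issue.

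The 27-day figure rests on nominal visit days, 28-day cycles and Table 16 read as written. Untested time at 320 mg as such is confined to the Cycle 3 Day 2 corner case.

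A reader might also infer that the SAP laboratory list omits these enzymes. It does not: SAP 10.3 refers to Protocol Table 11, which names both.

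**What to change.** Reconcile Section 7.3 with Table 16 and footnote k so that the Segment 2 DLT window closes with an amylase and lipase value:

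- Mark both analytes in Table 16 on Cycle 4 Day 1 for Segment 2, and at EOT for patients who stop before then. Chemistry blood is already drawn at both visits.
- Move or reword the Section 7.3 line so that it is clear whether it applies to visits other than Day 1.
- State whether the escalation-linked PK and PD visits in Tables 18 and 21 carry these tests.
- Align footnote k with the result.

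SAP 10.3 needs no change. The cost is two extra analytes on existing blood draws and a table, footnote and text edit, with no added visit for the Cycle 4 Day 1 or EOT samples. The downside is a few more incidental elevations for investigators to assess.
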